#### 11.1.1. Tumor Assessments

For tumor assessment, all sites of disease should be assessed radiologically by CT or MRI at screening and after every even cycle for the first 9 months of the study (ie, approximately every 6 weeks) and after every third cycle (ie, approximately every 9 weeks) thereafter while receiving study drug, until the occurrence of disease progression (see [Table 9-1](#)). CT or MRI scans obtained prior to informed consent will not need to be repeated if performed within 14 days prior to dosing. Brain scans performed as standard of care prior to informed consent will not need to be repeated if performed within 28 days prior to dosing. Assessments should be performed within 7 days prior to starting the subsequent cycle. Additional scans may be obtained at the discretion of the investigator, if clinically indicated. If a patient shows a radiological response (CR or PR), a confirmatory radiological assessment will be performed at least 4 weeks after the response was first noted. For patients who have a confirmed CR, it is strongly recommended that they receive PCI after completion of chemotherapy. Patients with a confirmed PR should also consider PCI after completion of chemotherapy based on the investigator's judgment (see [Section 8.8](#)). Following the completion of the induction part, PCI may be administered concurrently with atezolizumab during the maintenance part. For those patients who have not progressed at the time of study drug discontinuation, tumor assessments, including all sites of disease, will be assessed radiologically by CT or MRI, as performed at screening, every 2 months (approximately  $60 \pm 7$  days) until the occurrence of progressive disease or study completion.

The same method of assessment (CT or MRI) should be used to characterize tumors at screening and at all follow-up assessments. If PET is used, it should also be accompanied by spiral CT or MRI.

Investigators should follow the RECIST v1.1 guidelines ([Eisenhauer 2009](#)) for tumor assessments.

#### 11.1.2. Tumor Lesions: Identification and Follow-up

##### 11.1.2.1. Measurable Lesions

Measurable tumor lesions are defined as tumor lesions with a longest diameter (measured in at least 1 dimension) with a minimum size as follows ([Eisenhauer 2009](#)):

- 10 mm by CT or MRI (with a scan slice thickness of no greater than 5 mm)

Measurable lymph nodes must be  $\geq 15$  mm on the short axis by CT or MRI (with a scan slice thickness of no greater than 5 mm); only the short axis is to be measured at baseline and follow-up.

Lytic bone lesions or mixed lytic-blastic lesions with a soft tissue component meeting the definition of measurability above can be considered measurable lesions. Cystic lesions representing cystic metastases that meet the definition of measurability described above can be considered measurable lesions. If present, noncystic lesions should be selected as target lesions for this study.

A tumor lesion that has been previously irradiated may be considered measurable if unequivocal growth of the lesion has been demonstrated.

**Target lesions:** At baseline, up to 5 measurable tumor lesions/lymph nodes (with a maximum of 2 lesions per organ) should be identified as target lesions that will be followed to quantitate the status of disease during the study. Lesions with the longest diameter, that are representative of all involved organs, and for which reproducible repeated measurements can be obtained should be selected as the target lesions.

At baseline and each follow-up time point (see [Table 9-1](#)), each target lesion should be measured and the overall tumor burden will be calculated as the sum of the diameters of the target lesions (longest diameter [LD] for tumor lesions and short axis for lymph nodes) and documented in the eCRF. If a target lesion fragments into multiple smaller lesions, the LDs of all fragmented portions are added to the sum of the diameters. If multiple lesions coalesce, the LD of the coalesced lesion will be included in the sum of the diameters.

#### 11.1.2.2. Nonmeasurable Lesions

Nonmeasurable lesions include tumor lesions with a longest diameter  $< 10$  mm, lymph nodes with  $\geq 10$  to  $< 15$  mm short axis, or nonmeasurable lesions such as leptomeningeal disease, ascites, pleural or pericardial effusion, inflammatory breast disease, lymphangitic involvement of skin or lung, or abdominal masses/abdominal organomegaly identified by physical exam that is not measurable by CT scan or MRI ([Eisenhauer 2009](#)).

**Nontarget lesions:** All other lesions (or sites of disease) identified at baseline should be identified as nontarget lesions and recorded in the eCRF. Measurements of these lesions are not required, but the presence, absence, or unequivocal progression of each nontarget lesion should be recorded in the eCRF at each follow-up time point. Multiple nontarget lesions in the same organ may be noted as a single item on the eCRF.

#### 11.1.2.3. New Lesions

Any new lesions should be identified and recorded at each follow-up assessment, as these are markers of disease progression. As defined in the RECIST v1.1 guidelines ([Eisenhauer 2009](#)), new lesions include the following:

- A lesion in an anatomical location that was not scanned at baseline

- Equivocal new lesion of small size that with continued therapy and follow-up is found to progress and represent new disease (progression should be considered as of the date of the initial scan)
- Negative positron emission tomography with 2-deoxy-2-[fluorine-18]fluoro-D-glucose (FDG-PET) at baseline, but has a positive FDG-PET at follow-up
- No FDG-PET at baseline and a positive FDG-PET at follow-up that corresponds to a new site of disease as confirmed by CT (date of disease progression should be the date of the initial abnormal FDG-PET scan)

Note: Findings attributable to differences in scanning technique or a change in type of imaging (CT versus MRI) and findings representing something other than tumor (eg, healing or flare of existing bone lesions, necrosis of a liver lesion) should not be considered new lesions.

### 11.1.3. Definitions of Tumor Response and Disease Progression

The determination of SCLC tumor response and progression will be based on the RECIST v1.1 criteria ([Eisenhauer 2009](#)). The definitions for tumor response per the RECIST v1.1 criteria are as follows:

#### 11.1.3.1. Evaluation of Target Lesion Response

- **Complete response (CR):** Disappearance of all target lesions. Any pathological lymph nodes (whether target or nontarget) must have reduction in short axis to < 10 mm.
- **Partial response (PR):** At least a 30% decrease in the sum of diameters of target lesions, taking as reference the baseline sum of diameters.
- **Progressive disease (PD):** At least a 20% increase in the sum of diameters of target lesions, taking as reference the smallest sum on study (this includes the baseline sum if that is the smallest on study). In addition to the relative increase of 20%, the sum must also demonstrate an absolute increase of at least 5 mm. The appearance of 1 or more new lesions is also considered progression.
- **Stable disease (SD):** Neither sufficient shrinkage to qualify for PR nor sufficient increase to qualify for PD, taking as reference the smallest sum of diameters while on study.

A response category of not evaluable (NE) is to be used when there is inadequate information to otherwise categorize the response status.

#### 11.1.3.2. Evaluation of Nontarget Lesions

- **Complete response (CR):** Disappearance of all nontarget lesions and normalization of tumor marker level. All lymph nodes must be < 10 mm short axis.
- **Non-CR/Non-PD:** Persistence of 1 or more nontarget lesions and/or maintenance of tumor marker level above the normal limits.
- **Progressive Disease (PD):** Unequivocal progression of existing nontarget lesions or the appearance of at least 1 new lesion.

### 11.1.3.3. Evaluation of Overall Response

Patients who have at least 1 postdose tumor assessment (CT scan or MRI) will be considered evaluable for tumor response.

Table 11-1 describes the evaluation of overall response at each time point based on target and nontarget lesion responses at each time point, as well as the appearance of new lesions. The best overall response is the best response recorded from the start of the treatment until disease progression. Confirmation of CR and PR is required as described in Sections 11.1.3.1 and 11.1.3.2.

**Table 11-1 Evaluation of Overall Response at Each Time Point**

Target Lesions	Nontarget Lesions	New Lesions	Overall Response
CR	CR	No	CR
CR	Non-CR/Non-PD	No	PR
CR	Not evaluated	No	PR
PR	Non-PD/not evaluated	No	PR
SD	Non-PD/not evaluated	No	SD
NE	Non-PD	No	NE
PD	Any	Yes or No	PD
Any	PD	Yes or No	PD
Any	Any	Yes	PD

CR = complete response, PR= partial response, SD = stable disease, PD = progressive disease, NE = not evaluable  
 Source: (Eisenhauer 2009)

### 11.1.4. Treatment Beyond Disease Progression Per RECIST Version 1.1

Evidence indicates some patients treated with immunotherapy may derive clinical benefit after initial evidence of apparent disease progression (Wolchok et al 2013; Nishino 2013). Therefore, study drug administration may be continued until loss of clinical benefit, provided the patient appears to be deriving clinical benefit, the investigator believes it is in the best interest of the patient to continue and the patient has provided re-consent. Study drug administration refers to trilaciclib or placebo + E/P/A during the induction part or atezolizumab during the maintenance part. Treatment past disease progression per RECIST v1.1 should only be considered if a patient is clinically stable and has the following:

- Evidence of clinical benefit as assessed by the investigator
- Absence of symptoms and signs (including worsening of laboratory values; eg, new or worsening hypercalcemia) indicating unequivocal progression of disease
- No decline in ECOG performance status that can be attributed to disease progression
- Absence of tumor growth at critical anatomical sites (eg, leptomeningeal disease) that cannot be managed by protocol-allowed medical interventions
- All patients continuing treatment beyond progression must sign a separate written consent to acknowledge deferring alternative potential treatment options in favor of continuing study treatment at the time of initial apparent progression.

The assessment of clinical benefit should take into account whether the subject is clinically deteriorating and unlikely to receive further benefit from continued treatment. Decisions to

continue treatment beyond initial progression per RECIST v1.1 may be discussed with the medical monitor and should be documented in the study records.

Patients with radiographic disease progression confirmed at a subsequent tumor assessment may be considered for continued study treatment at the discretion of the investigator if they continue to meet the criteria above and have evidence of clinical benefit.

Immune-related disease progression (irPD) must be confirmed with worsening of disease bulk on the next tumor assessment, performed at least 4 weeks after the disease progression by RECIST v 1.1 was first noted. If the criteria of worsening disease bulk are met on 2 consecutive scans, the patient is determined to have confirmed irPD. If following an initial progression, the patient has a subsequent immune-related response (immune-related CR, PR or SD; determined from baseline), then the original progression is not confirmed and the patient may continue to receive study treatment and any subsequent progression must be confirmed on the next consecutive tumor assessment.

Confirmation of progression due to worsening disease bulk is defined as an additional 20% or greater increase in tumor burden volume from the time of initial RECIST v1.1 defined progression (including all target lesions and new measurable lesions) or an unequivocal further increase in nontarget lesions. In addition to the relative increase of 20%, the sum must also demonstrate an absolute increase of at least 5 mm. New lesions are considered measurable at the time of initial progression if the longest diameter is at least 10 mm (except for pathological lymph nodes, which must have a short axis of at least 15 mm). Any new lesion considered nonmeasurable at the time of initial progression may become measurable and therefore included in the tumor burden measurement if the longest diameter increases to at least 10 mm (except for pathological lymph nodes, which must have an increase in short axis to at least 15 mm).

For statistical analyses that include the investigator-assessed progression date, subjects who continue treatment beyond initial investigator-assessed, RECIST v1.1-defined progression will be considered to have investigator-assessed progressive disease at the time of the initial progression event. For patients who continue on treatment beyond RECIST v1.1-defined progression and have confirmed irPD, the date of the previous irPD will be recorded as the irPFS date.

## **11.2. Pharmacokinetic Assessments**

In a subgroup of at least 5 patients in each treatment group of the study, blood samples will be collected for the measurement of trilaciclib, etoposide, and carboplatin concentrations in plasma at the time points outlined below and in [Table 9-1](#). The sites identified to participate in the trilaciclib, etoposide, and carboplatin PK substudy will be based on the site's ability to complete all PK assessments. Sites will be identified during the site selection process. All patients in each treatment group will have blood samples collected for the measurement of atezolizumab plasma concentrations. Comprehensive information on blood sample acquisition, the specific type of collection tube with anticoagulant, and handling and storage are to be found in the Laboratory Manual. The analytical laboratory will measure plasma concentrations of trilaciclib, etoposide, carboplatin, and atezolizumab using validated

methods. Any remaining samples may be stored long term (up to 10 years) for the future analysis of trilaciclib drug metabolites.

Day 1 of Induction Cycles 1 and 3

Blood samples will be collected at the following time points on Day 1 of Induction Cycles 1 and 3 for all patients enrolled in the PK subgroup of the study: predose (0 hour; prior to dosing of trilaciclib or placebo) and at 0.5 (end of infusion [EOI] of trilaciclib or placebo), 1 (EOI of carboplatin), 2 (EOI of etoposide), 4, 6, and 24 (prior to trilaciclib or placebo dose on Day 2) hours. The EOI sample for trilaciclib or placebo should be drawn 2 to 5 minutes prior to the EOI. The EOI samples for trilaciclib or placebo, carboplatin, and etoposide must be drawn after completing infusion of the drugs and the actual times at which the samples were drawn should be documented. A  $\pm$  5-minute time window will be allowed for samples collected between the following time points: predose to 2 hours after the end of trilaciclib or placebo infusion. A  $\pm$  10-minute time window will be allowed for samples collected between the following time points: 4 to 6 hours after the end of trilaciclib or placebo infusion. A  $\pm$  1-hour time window will be allowed for the 24-hour time point. The actual time of blood sample collection should be documented in the eCRF. The Induction Cycle 1 Day 1 sampling scheme is summarized in [Table 11-2](#).

**Table 11-2 Day 1 of Induction Cycles 1 and 3 Blood Sampling Scheme Based on Predicted Administration Times of Trilaciclib/Placebo, Carboplatin, and Etoposide**

Sample	1	2	3	4	5	6	7
Sample Time (h) from start of trilaciclib/placebo infusion	0 (Predose a )	0.5 b (Trilaciclib /Placebo EOI c )	1.0 (Carbo EOI c )	2.0 (Etop EOI c )	4.0 d	6.0 e	24 f (prior to trilaciclib dose on Day 2)

Carbo = carboplatin; EOI = end of infusion; Etop = etoposide; h = hour

Times are approximate. For simplicity, assumptions were based on 0.5 hour infusion of trilaciclib/placebo. Actual times will be recorded and may vary from those listed here.

- a Predose is defined as prior to initiation of trilaciclib/placebo administration.
- b The EOI sample for trilaciclib should be drawn 2 to 5 minutes prior to the EOI.
- c Trilaciclib/placebo – 30-minute infusion; carboplatin infusion = 30 minutes; etoposide infusion = 60 minutes
- d Sample #5 to be collected 4 hours from the start of trilaciclib/placebo infusion (eg, 3.5 hours from trilaciclib/placebo EOI)
- e Sample #6 to be collected 5 hours from the start of trilaciclib/placebo infusion (eg, 4.5 hours from trilaciclib/placebo EOI)
- f Sample #7 to be collected prior to initiation of trilaciclib/placebo Day 2 dose

If it is necessary to slow the infusion rate of any of the study drugs at a given visit for a particular patient, the collection time of any subsequent PK sample(s) should be adjusted accordingly to ensure that the sample is collected at the actual EOI (trilaciclib/placebo, carboplatin, and/or etoposide). Please continue to use the sample labels with the scheduled time; however, ensure that actual time of sample collection is recorded appropriately on the eCRF.

Day 1 of Induction Cycles 1, 2, 3, and 4; Maintenance Cycles 4, 8, 12, and Every Eighth Cycle Thereafter; and at 30 and 90 Days After the Last Dose of Study Drug

Blood samples will be collected at the following time points relative to atezolizumab infusion to determine the minimum and maximum observed serum atezolizumab concentration: predose and 30 minutes after the end of the atezolizumab infusion.

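### Protocol Section 11.2 tells sites to draw the trilaciclib/placebo end-of-infusion PK sample both before and after the infusion ends, and Table 11-2 gives two different times for sample 6

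*Protocol*

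**What the plan says.** Protocol Section 11.2 sets the blood sampling for trilaciclib, etoposide and carboplatin on Day 1 of Induction Cycles 1 and 3: "In a subgroup of at least 5 patients in each treatment group of the study".

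**EOI sample.**
- Section 11.2 says "The EOI sample for trilaciclib or placebo should be drawn 2 to 5 minutes prior to the EOI". The synopsis (Pharmacokinetics Evaluation) has the same instruction, and footnote b of Table 11-2 says "The EOI sample for trilaciclib should be drawn 2 to 5 minutes prior to the EOI".
- The next sentence of Section 11.2 says "The EOI samples for trilaciclib or placebo, carboplatin, and etoposide must be drawn after completing infusion of the drugs".
- The text below Table 11-2, on infusions that have to be slowed, uses a third wording: the sample is to be taken at the moment the infusion actually ends.

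**Sample 6.** The synopsis, the Section 11.2 text and the Table 11-2 column all give 6 hours. Footnote e, attached to that column, gives 5 hours from the start of infusion, with 4.5 hours from EOI as its example.

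**Windows.** Section 11.2 allows ±5 minutes for samples from "predose to 2 hours after the end of trilaciclib or placebo infusion" and ±10 minutes for samples from "4 to 6 hours after the end of trilaciclib or placebo infusion". The synopsis and Table 11-2 count the sample times from the start of infusion, not the end.

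**The concern.** The two EOI sentences stand next to each other, and the second names trilaciclib or placebo, so it cannot be read as covering carboplatin and etoposide only. A site that follows one breaks the other. The before-EOI instruction appears in three places but is phrased as a recommendation; the after-EOI instruction appears once but is phrased as an obligation. Neither frequency nor strength of wording decides between them.

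Table 11-3 defines Cmax as an observed peak. The 0.5-hour draw is the only one scheduled near the end of the trilaciclib infusion; the next is at 1.0 hour. If sites resolve the conflict differently, Cmax will be read before EOI in some patients and after it in others. Recorded times would show which side a draw fell on, but they cannot supply the value that was not sampled.

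For sample 6, Protocol Section 13.7 tabulates concentrations by visit and time point. If some sites draw at 5 hours and others at 6, one nominal time point would hold both.

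**Working it through.** There is no planned figure to reproduce. The check compares the passages and converts between the two clocks: time from EOI = time from start − infusion length.

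**Input.** Infusion length is 0.5 h = 30 minutes, the assumption stated under Table 11-2.

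**EOI sample, in minutes from the start**
- Before-EOI rule: 30 − 5 = 25 to 30 − 2 = 28.
- After-EOI rule: later than 30.
- Overlap: none.
- Window around the nominal 0.5 h: 30 ± 5 = 25 to 35. This spans both sides of EOI, so it tolerates either reading and does not choose between them.

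**Sample 6**

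| Source | From start | From EOI |
|---|---|---|
| Synopsis, Section 11.2 text, Table 11-2 column | 6.0 h | 6.0 − 0.5 = 5.5 h |
| Table 11-2 footnote e | 5.0 h | 5.0 − 0.5 = 4.5 h |

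Footnote e agrees with its own example of 4.5 h, so the 5-hour figure runs through the whole footnote and is not a slip in one number. Footnote d provides a comparison: "Sample #5 to be collected 4 hours from the start of trilaciclib/placebo infusion", with 4.0 − 0.5 = 3.5 h from EOI, which agrees with its column. The gap for sample 6 is (6 − 5) × 60 = 60 minutes. The permitted deviation is ±10 minutes, so no draw lies within the window of both times.

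**Window clock (secondary).** Sample 5 falls 3.5 h after EOI. Counted from EOI, as Section 11.2 literally says, that lies between the end of the ±5-minute range (2 h) and the start of the ±10-minute range (4 h), so no window covers it. Counted from the start, 4 h falls in the ±10-minute range, which is probably what is meant.

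**Amount of data exposed.** Trilaciclib concentrations come from the active group. At the minimum of 5 patients sampled in two cycles, that is 5 × 2 = 10 scheduled EOI draws.

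**The case against.** The case for leaving the text alone has several parts.

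- **Times are approximate.** The note under Table 11-2 says so and says that actual times will be recorded. This softens the 60-minute gap for sample 6, since AUC and the terminal slope can be computed from recorded times. It does not touch the EOI conflict, which is about order: before or after the infusion ends.
- **The Laboratory Manual may settle it.** Section 11.2 refers sites there: "Comprehensive information on blood sample acquisition, the specific type of collection tube". The manual is not among the documents. If it gives one rule, practice may be uniform, but the protocol would still contradict itself.
- **The subgroup may be larger.** The text after Table 11-3 allows samples from additional patients, so 5 per group is only a minimum. Section 9 also allows PK timing to change without an amendment under stated conditions. Neither provision removes the conflict.
- **The consequence is small.** PK is descriptive. SAP Sections 3.1.6 and 6.2.10 place it in a separate document. This stands, and it is why the point is minor.

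Two stronger readings are tempting. A reader might try to attach a percentage error to Cmax or to the 5-hour versus 6-hour difference. Protocol Section 4.3.1 reports a terminal half-life and three-compartment kinetics but no distribution half-life, and it reports AUC rising more than in proportion to dose. Any percentage would rest on linear kinetics, which that finding puts in doubt, or on parameters the documents do not give.

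A reader might also infer from the median Tmax of 0.25 to 0.47 h in Section 4.3.1 (15.0 to 28.2 minutes, before nominal EOI) that the before-EOI rule is the intended one. That study's sampling times are not given, so the figure cannot decide the matter.

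**Conclusion.** The protocol is wrong as written on two points: the EOI instructions for trilaciclib/placebo cannot both be followed, and footnote e disagrees with its own column and with the text. Both conflicts are in current, legible text, and no other passage resolves either. The mismatch between the window clock and the sample clock is a secondary drafting fault.

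Severity is minor. Confidence is high that the text conflicts; how far it affects results is unknown. Mixing of Cmax draws, or of 5-hour and 6-hour draws, is possible but not shown, because it depends on what sites do and on what the Laboratory Manual says. Its size cannot be derived from the documents. The primary and key secondary analyses, the sample size and the type I error are unaffected. The arithmetic rests only on the 30-minute infusion that Table 11-2 itself assumes. This review does not say which EOI rule or which sample 6 time is intended.

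**What to change.** 1. The sponsor confirms one rule for the trilaciclib/placebo EOI sample and states it identically in the synopsis, the Section 11.2 text, footnote b of Table 11-2 and the slowed-infusion text below that table.
2. Footnote e is reconciled with the Table 11-2 column, the Section 11.2 text and the synopsis, for both its time from start and its time from EOI.
3. The sampling windows are stated on the same clock as the sample times, namely from the start of infusion.
4. The Laboratory Manual is checked for agreement with the reconciled text.

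The cost is wording in the synopsis, Section 11.2 and Table 11-2, plus the manual check. No extra samples or visits are needed. Where samples have already been drawn, the recorded times can show which side of EOI each draw fell on and whether sample 6 was taken nearer 5 or 6 hours. The PK report can state this.
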